1. INTRODUCTION

Study FGCL-3019-079 has reached DBL and an interim CSR has been completed. There was an error in p-value reporting in the original SAP which requires an amendment to all related tables and figures. The update is provided in this SAP addendum.

Furthermore, as ADA samples were analyzed after the interim CSR, the analysis and reporting of ADA will be included in this SAP.

2. UPDATE TO THE ORIGINAL SAP

Reason for change:

The original approved SAP (version 1.0, dated June 25, 2020) specified 2-sided p-values to be reported for confidence intervals. However, the SAS function PROBT specified in SAP version 1.0 Appendix 1 and errata to the SAP returned a 1-sided p-value. The following amendments are made to correct related p-values.

In SAP Appendix I (on page 24, box on the left side below): the δ (or delta) should be (m_1-m_2) and t-test statistics should be $(m_1-m_2)/se$.

Two Sample Test statistics $\delta = \frac{(m_1-m_2)}{se}$
 
T-test:
 
95% CI: $\delta \pm t(\delta, df) * se$
 
$p = t(\delta, df)$ (SAS function: probt(δ, df)).
 
Please note that if $\delta \leq 0$, p-value=p; if $\delta > 0$, p-value=$1-p$.
	
ERRATA TO THE SAP
 
Two Sample Test statistics, $\delta = (m_1-m_2)$
 
T-test: $t = (m_1-m_2)/se$
 
95% CI: $\delta \pm tinv(0.975, df) * se$
 
(SAS function: $p = probt(t, df)$ to get the p-value for the t-test.
 
Please note that if $\delta \leq 0$, p-value=p; if $\delta > 0$, p-value=$1-p$.

--	--

In Errata to SAP (on Page 38, right side box above), which was not signed off with any signatories, δ (or delta) and t-test statistics were corrected, however, the p-value was still 1-sided.

To correct this 1-sided p-value issue, the following highlighted in yellow is the only update to the Errata to SAP, where the p-value is multiplied by 2 and clarified as “2-sided”.

(SAS function: $p = 2 * probt(t, df)$ to get the **2-sided** p-value for the t-test.

Please note that if $\delta \leq 0$, p-value= p ; if $\delta > 0$, p-value= $1-p$.

In addition, in section 4.6.6.2 of the original SAP, the sentence “the results for the PUL total score will be compared with the results from Ricotti, 2019” shall be removed, since different versions of PUL were used.

Since all secondary endpoints are “Change from Baseline to Week 104”, the estimate of annual change for some secondary endpoints will not be reported due to data and/or analysis model limitations.

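### The SAP Addendum's corrected two-sided p-value rule returns a negative number whenever the difference between means is positive

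*SAP*

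**What the plan says.** Section 2 of the SAP Addendum explains that SAP version 1.0 "specified 2-sided p-values to be reported for confidence intervals", but that the SAS function it named, in both its Appendix 1 and the later errata, "returned a 1-sided p-value". It shows the two versions of the two-sample test side by side and then gives its own correction.

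- From the errata it carries forward delta = m1 − m2, t = delta/se, and a 95% confidence interval of delta ± `tinv(0.975, df)`*se.
- The new definition of p is given as "SAS function: $p = 2 * probt(t, df)$ to get the" two-sided p-value.
- The line that follows is unchanged from the errata. When delta is zero or negative, p itself is reported. For a positive difference it reads "if $\delta > 0$, p-value=$1-p".

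The scope of the change is explicit: "the following highlighted in yellow is the only update to the Errata to SAP, where the p-value is multiplied by 2". The addendum's Introduction adds that the error means all related tables and figures have to be amended.

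**The concern.** `probt` is the lower-tail cumulative probability of the t distribution. Switching to 1 − p for positive t is the right way to get the upper tail when p is that probability. Once p has been doubled, 1 − p no longer has that meaning: for positive t the doubled value exceeds 1, and subtracting it from 1 gives a negative number.

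The addendum exists largely to correct this one formula, and it governs the amended tables. If the formula is programmed as displayed, every two-sample comparison with m1 > m2 prints an impossible p-value, and any automatic check for p < 0.05 treats all of them as significant. If a programmer notices and repairs it silently, the reported values no longer follow the signed plan. The text needs correcting in either case.

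**Working it through.** **Inputs.** All come from section 2 of the SAP Addendum: t = (m1 − m2)/se, so t has the sign of delta; p = `2*probt(t, df)`; report p if delta ≤ 0 and 1 − p if delta > 0. The documents give no t values or degrees of freedom, so those below are assumptions used for illustration. Write F for `probt(t, df)`.

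**Step 1: reproduce the addendum's diagnosis.** The errata rule reports F for t ≤ 0 and 1 − F for t > 0. Both equal P(T > |t|), the one-sided tail. At df = 40, t = −2 and t = +2 each give 0.0262, and the two-sided value is 0.0523. The addendum is right that the errata rule is one-sided.

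**Step 2: apply the addendum rule as written.**

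- For t ≤ 0 it reports 2F, which is the correct two-sided p-value.
- For t > 0 it reports 1 − 2F. The correct value is 2(1 − F) = 2 − 2F. The reported value is therefore the correct value minus 1. Since F > 0.5 whenever t > 0, it is always negative, whatever the degrees of freedom.

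| df | t | Addendum rule | Correct two-sided p |
|---|---|---|---|
| 40 | −2.5 | 0.0166 | 0.0166 |
| 40 | −2.0 | 0.0523 | 0.0523 |
| 40 | +0.5 | −0.3802 | 0.6198 |
| 40 | +1.0 | −0.6767 | 0.3233 |
| 40 | +2.0 | −0.9477 | 0.0523 |
| 40 | +2.5 | −0.9834 | 0.0166 |
| 20 | +2.0 | −0.9407 | 0.0593 |
| 100 | +2.0 | −0.9518 | 0.0482 |

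A grid over df 1 to 200 and t from 0.0001 to 8 gave a negative value at every point and matched the identity (correct p minus 1) to rounding error. On the mirrored negative t values the rule was correct throughout.

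**Step 3: consequence for a p < 0.05 flag under a true null.** The flag fires when t ≤ 0 and 2F < 0.05, which has probability 0.025, or whenever t > 0, which has probability 0.50. The total is 0.025 + 0.50 = 0.525, against the nominal 0.05.

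**Step 4: alternative reading of p.** Suppose p in the reporting line means the undoubled F. The rule then reports F or 1 − F, which is the one-sided errata rule again, and the correction has no effect.

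**The case against.** The best defence is the addendum's prose. It speaks of the p-value being multiplied by 2, and in the errata the p-value is what comes out after the choice between p and 1 − p. Doubling that final quantity gives the correct two-sided result for both signs, and the two-sided intent is unmistakable. A programmer working from the prose could get it right. But the displayed formula puts the factor of 2 before the choice, and it is the only specification of how the doubling is done. So the prose shows what was meant without repairing the rule.

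The limits on reach do stand:

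- The rule applies to two-sample p-values in a single-arm study. The primary criterion (Protocol 9.4.1) rests on the lower bound of the 95% confidence interval for the mean annual change, not on this p-value.
- The errata's confidence interval does not use p and is sound.
- The open-label extension comparison with natural history data takes its tests from the mixed model (SAP Appendix 2) and is unaffected.
- No output is included, so the documents cannot show that any negative p-value was printed. The 52.5% figure depends on literal programming and an unchecked significance flag, and is not the trial's type I error rate.
- The addendum does not say which group is m1. Even if m1 is pamrevlumab, a positive difference is unfavourable on endpoints where higher is worse, such as the cardiac fibrosis score. The direction in which the error would mislead is therefore not known.

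**Conclusion.** The rule is wrong as written. For every positive delta it returns the true two-sided p-value minus 1, an impossible negative number; for delta of zero or below it is correct. This follows from the algebra alone and does not depend on the degrees of freedom. The worked values rest on assumed degrees of freedom and t values, and the 52.5% rate assumes literal programming with an automatic p < 0.05 flag. The error affects only the two-sample p-values covered by the addendum. SAP version 1.0, which would show which comparisons these are, is not among the documents reviewed. The limited reach does not make the correction optional, because this formula is the one the addendum was issued to put right and the amended tables depend on it.

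**What to change.** Replace the definition of p and both delta branches with one line: two-sided p = `2*(1 - probt(abs(t), df))`. This is valid for either sign of t. At df = 40 it gives 0.3233, 0.0523 and 0.0046 for |t| = 1, 2 and 3.

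Then check every affected p-value against its interval, delta ± `tinv(0.975, df)`*se: p should be below 0.05 exactly when the interval excludes 0. If the tables were already produced with a corrected formula, say so in the amended text so that plan and output agree.

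The cost is one line of addendum text, one line of code, and a re-run or check of the tables the addendum already says must be amended. A further signed version of the addendum may be needed, since database lock and the interim study report came before it and the documents do not say whether the tables have since been re-issued.

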3. IMMUNOGENICITY ANALYSIS

3.1. Immunogenicity Analysis Set (IGS)

The Immunogenicity Analysis Set (IGS) contains all the ADA/NAb evaluable patients, who are in the SAF analysis set with at least one ADA/NAb sample (with reportable results) taken pre-treatment (i.e., a baseline sample) and at least one ADA/NAb sample (with reportable result) taken post-treatment.

Analysis of immunogenicity data will be based on IGS. Analysis dataset and data listing will include all available Human Anti-Human Antibody (HAHA, ADA) samples. The following terms and definitions are implemented.

3.2. Terms and Definitions

3.2.1. Sample ADA Status:

- Baseline ADA-positive sample: ADA is detected in the last sample before initiation of treatment.
- Baseline ADA-negative sample: ADA is not detected in the last sample before initiation of treatment.
- **Treatment-emergent ADA-Positive:** Meets the definition of treatment-induced or treatment-boosted ADA. After initiation of treatment,
 - **Treatment-induced ADA-Positive:** a post-treatment positive ADA is detected in a subject for whom pre-treatment ADA assessment is either negative or not assessable, or
 - **Treatment-boosted ADA-Positive:** pre-existing ADA was boosted to a higher-level following study treatment, i.e. pre-treatment positive ADA titer was boosted by at least 2 dilution steps (4-fold) following study treatment.
- ADA-negative sample: After initiation of treatment, ADA is not treatment-emergent ADA-positive.

Next, using the sample ADA status, subject ADA status is defined.

3.2.2. Subject ADA Status:

- Baseline ADA-positive subject: A subject with baseline ADA-positive sample.
- ADA-positive subject: An evaluable subject with at least one treatment-emergent ADA sample at any time during the study.
- Neutralizing-positive: At least one treatment-emergent ADA-positive sample with neutralizing antibodies detected (if available).
- ADA-negative subject: An evaluable patient without a treatment-emergent ADA sample during the study.

3.3. Statistical Analysis for Characterization of ADA Immune Response

3.3.1. Incidence of ADA

- Percentage of treatment-emergent ADA patients for the defined study period, where the denominator is the number of ADA evaluable patients in the respective treatment arm and/or subgroup.
- Number (%) of subjects will be reported for the following parameters based on evaluable subjects:
 - Baseline ADA-positive
 - ADA-positive (Treatment-induced, Treatment-boosted)
 - Neutralizing Positive (if available)
 - ADA-negative
- **ADA prevalence:** Percentage of treatment-emergent ADA patients at any given timepoint, where the denominator is the number of ADA evaluable patients in the respective treatment arm and/or subgroup at that timepoint.
- A listing of all ADA assessments will be provided.
- Additionally, a separate listing of ADA assessments for all neutralizing antibody (NAb)-positive subjects will be provided (if available).

3.3.2. ADA Titer Kinetics

All ADA-positive subjects will be included in the analysis.

- Summary statistics of subject-level ADA titers using the maximum titer value within an ADA positive subject will be presented for baseline ADA-negative subjects and baseline ADA positive subjects. The median, interquartile range, and range of the maximum titers will be reported. For ADA-positive subjects with baseline ADA-positive samples, the median and interquartile range of the fold increase from baseline in titer (ratio of maximum post-baseline titer to baseline titer) will also be reported. Graphical presentation of the summary data may be provided using boxplots, as appropriate.
- For sample-level ADA titers, boxplots of ADA titers at each assessment timepoint will be provided, as appropriate, to demonstrate whether the ADA levels tend to change over time during the treatment, along with ADA incidence at each assessment timepoint.
- Spider plots may be considered to show the trend of ADA titer over time for subjects with ≥ 5 ADA results by splitting subjects into multiple spider plots (e.g., ≈ 10 per plot, approximately).

3.4. Clinical Implication of ADA Immune Response

3.4.1. Safety

- Effect of ADA response on safety will be explored by examining the frequency and type of AEs of interest, including (1) Total TEAEs, (2) Drug Hypersensitivity, and (3) Infusion Reactions. For each category of AEs, summary tables for incidence will be provided for each of the preferred terms and overall within a category by ADA status, if the number of ADA-positive subjects is of sufficient size (e.g., at least ≈ 10 subjects). Otherwise, individual subject's safety profile will be examined and described based on a listing.
- Listings of AEs will be provided. These listings will also indicate the study day and study period of the positive responses.

3.4.2. Efficacy

- The primary efficacy endpoint will be presented by ADA status.
- Efficacy listings for all positive subjects (relative to baseline) will be provided. These listings will also indicate the study day and study period of the positive responses.
